7.2 Assessment Time Windows

For calculations of all AUC endpoints (including the primary endpoint), rate of consumption of rescue and time to first rescue medication endpoints, the actual dates/times of the assessments will be used in calculations. Thus, while the NRS are intended to be collected at the pre-defined protocol scheduled time points (eg, Hour 0.5, 1, 2, etc.), it is recognized that operationally the scores are collected as close to the target times as possible but there is some flexibility in terms of the actual times the scores are collected. Thus, to account for this inherent aspect of data collection, the ACTUAL TIMES will be used for the calculation of the AUC. The actual times will be based relative to the time of completion of study drug administration.

Safety assessment summaries will be based on the nominal protocol-specified assessment times.

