After completing the assessments through T96h hours after study treatment administration and prior to discharge from the inpatient unit, review with the subject the use of a diary for at-home use to record pain assessments and medication use (including pain medication) at home.

Additionally, obtain the subject's global assessment of satisfaction with study treatment (patient global evaluation or PGE) and the investigator's global evaluation (IGE) prior to discharge. Finally, instruct subjects to return to the study center on D8 $\pm$ 1 for a follow-up assessment.

Once discharged from the inpatient unit, all study participants will be instructed to take a combination of OTC analgesics (NSAID and acetaminophen) at an appropriate dose per medical judgment to manage any residual or breakthrough postsurgical pain through D29/W4.

Outpatient period: D4 through D29/W4:

- If needed for pain management, over-the-counter (OTC) analgesics administered PO, e.g.,
  - NSAID (e.g., ibuprofen 200 mg to 400 mg prn qid [Advil® or Motrin®] or naproxen 220 mg prn tid [Aleve®]) or other options per investigator discretion **and**
  - Acetaminophen 1-2 500 mg tablets (up to 1 g) prn tid or 650 mg prn qid (3g daily limit)

- If a subject is still requiring opioid rescue in the 12h prior to discharge (i.e., from T84h on regardless of whether discharge is delayed), prescribe oxycodone 5 mg PO tid prn (medical discretion on dosing and number of tablets dispensed per consideration of subject's age/history and needs, but no more than six tablets should be prescribed and may be taken as needed over the next several days). If additional oxycodone is required, refills are left to investigator discretion.

Persistent pain or pain exacerbations during this period may suggest the need for an unscheduled in-person visit to assess the surgical site. If such a situation occurs, the Investigator should use clinical discretion on adequacy of analgesic treatment, but to capture this event as an adverse event (AE) and document any required treatments.

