#### **9.1.10. Unscheduled Visits**

Unscheduled visits may be scheduled at any time if warranted due to the subject's complaints or condition per investigator discretion. Assessments performed at Unscheduled Visits will be at the discretion of the investigator. If these visits occur prior to D29±2 (W4), perform the following:

- Record vital signs (HR, BP and RR)
- Interim PE focusing on the surgical site assessment and neurosensory exam of both feet (proximal to the surgical site)
- Concomitant Medication Use including doses and times taken for analgesic medications

- Concomitant Treatments including topical ice pack or cooling treatments
- AE Assessment

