3 GENERAL ANALYSIS AND REPORTING CONVENTIONS

This section discusses general policies to be employed in the analysis and reporting of the data from the study. Departures from these general policies may be provided in the specific detailed sections of this SAP. When this situation occurs, the rules set forth in the specific section take precedence over the general policies.

Each active dose will be presented separately in summaries and analyses as appropriate.

All continuous study assessments will be summarized by treatment and time point (as applicable) using the descriptive statistics n, mean, SD, median, and range (minimum, and maximum). All of the categorical study assessments will be summarized by treatment and time point (as applicable) using frequency counts and rates of occurrence (%). Changes from baseline for continuous outcomes will be presented as their corresponding continuous measures for post-baseline visits. All study data will be listed by dose, subject, and time point (as applicable).

No preliminary rounding will be performed; rounding will only occur after the analysis. To round, consider the digit to the right of the last significant digit: if <5, then round down; if ≥5, then round

up. Means and medians will be presented with one more decimal place than the precision of the data. Standard deviations will be presented with two more decimal places than the precision of the data. Percentages will be presented with one decimal place. A percentage of 100% will be reported as 100%. Minimums and maximums will be presented with the same precision as the original data.

All analyses will be performed using the SAS System® version 9.3 or higher. The domain (Study data tabulation Model [SDTM]) and analysis (Analysis Data Model [ADaM]) data sets will be taken as input to the SAS programs that generate the report-ready tables, figures and listings. The submission ready SDTM and ADaM data sets will be provided to the sponsor along with display deliveries.

The following conventions will be used throughout the study analysis:

- Time 0 (T0) is the time of completion of study drug administration.
- Day of surgery is defined as Day 0 (D0).
- Assessment visit times are defined by D0 and/or T0.
- Baseline value is defined as the last valid measurement prior to the dosing of study treatment.
- Change from baseline is defined as post-baseline value minus baseline value.

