8.3 Surgical Site Assessment/ Wound Evaluation

Surgical site is defined as the area extending approximately 2-3 cm in all directions (lateral/medial/proximal/distal) from the incision site and surrounding tissues which may be affected by the infiltration of the Investigational Product.

At T96h prior to discharge, the investigator will evaluate their satisfaction with the healing of the wound during this Surgical Site assessment using an 11-point scale (0-10) where a score of 0 is "Completely unsatisfied," and a score of 10 is "Completely satisfied.". Surgical site wound status will be evaluated prior to discharge from the inpatient unit (T96h) and on Days 8, 15, and 29 or if necessary Day 36. Surgical site wound status will be assessed for erythema, drainage, edema, induration, and hematoma using a 5-point scale (0-4) where 0 means none and 4 means severe.

The surgical site and surgical wound assessment results will be listed and will be summarized by treatment and visit.

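### Unscheduled-visit wound and neurosensory results have no stated row in the safety tables, and no worst post-dose result per subject is planned

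*SAP*

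**What the plan says.** **Collection.** Protocol 9.1.10 opens: "Unscheduled visits may be scheduled at any time if warranted due to" the subject's complaints or condition, at the investigator's discretion. For such visits before Day 29 it lists: "Interim PE focusing on the surgical site assessment and neurosensory exam of both feet". The Schedule of Assessments (Table 1) marks both exams in its Unscheduled Visit column. Protocol 9.1.4 says that persistent or worsening pain after discharge "may suggest the need for an unscheduled in-person visit to assess the surgical site".

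**Summary.** SAP 7.2 uses actual times for the pain AUC, rescue-consumption rate and time-to-rescue endpoints, then says of safety: "Safety assessment summaries will be based on the nominal protocol-specified assessment times". SAP 8.3 gives the wound schedule: "Surgical site wound status will be evaluated prior to discharge from the inpatient unit (T96h) and on Days 8, 15, and 29", plus Day 36 if necessary. Five signs are graded "using a 5-point scale (0-4) where 0 means none and 4 means severe". The reporting rule is: "The surgical site and surgical wound assessment results will be listed and will be summarized by treatment and visit". SAP 8.6 treats the neurosensory exam in the same way, counting normal and abnormal results by arm, foot and time point. The general rule in SAP Section 3 agrees: "All of the categorical study assessments will be summarized by treatment and time point (as applicable) using frequency counts and rates of occurrence".

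**Displays.** The SAP's table list has one wound table (14.3.5) and two neurosensory tables (14.3.6.1 for the target foot, 14.3.6.2 for the other). Listings 16.2.24 and 16.2.25 carry the individual results.

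**The concern.** CA-008 is put directly into the wound and acts on sensory nerves. Wound healing and local sensation are therefore central safety questions, and both are listed as safety endpoints in their own right (Protocol 12.6.2, SAP 8.1). The exams most likely to find a problem are those held because the subject complained or the investigator was concerned. If their results have no row, a marked but short-lived finding can appear in a listing while every by-visit row for that subject looks clean.

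By-visit rows also do not say how many different subjects ever had a given grade. A reader comparing dose groups would want that count, and it cannot be recovered from the visit rows.

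**Working it through.** No figure in the plan bears on this point, so there is none to reproduce. The check compares where results are collected with where they are summarized, and then does simple arithmetic on the planned arm size.

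**1. Is there a row for unscheduled results?**
- Collected: yes, for both exams (Protocol Table 1 and 9.1.10).
- Summarized: no row is stated. SAP 7.2 ties safety summaries to nominal times, and an unscheduled visit has none. SAP Table 2-1, which sets out the protocol-specified visits, lists no unscheduled visit. SAP 8.3 and 8.6 name T96h and Days 8, 15, 29 and, if needed, 36; only 8.6 mentions early termination, joined to Day 29. SAP 2.2 says that unscheduled visits can occur, but no analysis section says how their results are tabulated.
- Moving such a result into a scheduled visit would not reliably keep it. For duplicate values at a visit, SAP Section 3 takes the last one, not the worst.

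**2. Is a worst result per subject planned?** Not for wound grade or neurosensory result, in the text or the table list. The only per-subject maximum is for AEs (SAP 8.2, Table 14.3.1.6).

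**3. What do the other routes catch?**
- Listings: every result, but with no count by arm.
- AE tables: Protocol 15.7.4 sends abnormal or clinically significant surgical-site findings to the AE record. Protocol 9.1.4 does the same for the persistent or worsening pain that may prompt a visit. SAP 8.2 counts each subject once per term at greatest severity, with no restriction to scheduled visits.
- Not caught: the 0-4 grade itself, because AE severity (mild to potentially life-threatening) is a different scale; a graded sign that the investigator regards as ordinary for this surgery; and numbness at or near the incision, which Protocol 12.5.8 says need not be an AE.

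**4. Size per subject.** With the planned 36 per arm, one subject is 1/36 = 2.8 percentage points. The Safety Population may differ slightly from 36.

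**5. How many subjects could be involved?** The documents give no rate of unscheduled visits. As an assumption, if 5%, 10% or 20% of subjects had at least one:
- 36 × 0.05 = 1.8 per arm
- 36 × 0.10 = 3.6 per arm
- 36 × 0.20 = 7.2 per arm

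These count subjects with a visit that has no stated row. The number with a finding missed at every scheduled exam can only be equal or smaller.

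**6. By-visit rows against subjects ever affected.** Suppose each of the four exams planned for everyone (T96h, Days 8, 15, 29) shows 1 of 36 with a high grade. That may be one subject four times (1/36 = 2.8%) or four subjects once each (4/36 = 11.1%). The planned table cannot tell these apart. This ambiguity concerns scheduled exams only and does not measure the unscheduled-visit gap.

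**The case against.** The strongest reply is that little is really lost. SAP 7.2 is a timing rule that contrasts clock times with nominal labels; it does not say that unscheduled results are dropped. Table 1 gives unscheduled visits their own column, so a programmer could add a row for them within the by-visit wording of SAP 8.3. Abnormal findings go to the AE record, AEs are tabulated at greatest severity, and everything is listed. Safety is descriptive, with no formal comparison.

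Most of this stands. A reader might infer that the SAP excludes unscheduled wound grades and that a subject's worst grade is never counted. The documents do not support that. The word only does not appear in the SAP 7.2 sentence, a worst grade seen at a scheduled exam is counted in that visit's row, and many findings at other visits will be counted as AEs. What remains is silence on placement, the lack of a per-subject worst result, and the findings that the AE route does not cover.

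Two further objections affect the remedy. First, the text does not expressly require Appendix F grading at unscheduled visits. Table 1 marks a surgical site assessment there, while 9.1.10 describes a focused exam and leaves assessments to discretion. A worst-grade panel can therefore use only the grades actually recorded. Second, subjects with more visits have more chances to score high. Pain is a named trigger, and Protocol 15.6 expects placebo subjects to use rescue more often. If visits cluster in placebo, a worst-over-all-visits row could make active treatment look better. This is a fair criticism of such a row shown alone.

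**Conclusion.** The concern holds as a gap in the reporting rules. Followed as written, the SAP gives unscheduled wound and neurosensory results no row in Tables 14.3.5, 14.3.6.1 and 14.3.6.2, and it produces no worst post-dose result per subject. AE tables and listings cover much of the gap, but not on the 0-4 wound scale and not for findings that need not be AEs.

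The size is unknown: 2.8 percentage points per affected subject in an arm of 36, with no documented rate to multiply it by. The direction between arms is also unknown. A reader might conclude that the wound table is biased in favor of CA-008, but the documents do not show which arms will have more unscheduled visits, and pain-driven visits could be commoner on placebo. The point does not touch the efficacy analyses. It is worth fixing because local tolerability is a main safety question here, and because a rule chosen after unblinding would be post hoc under SAP Section 1.

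**What to change.** Before unblinding:

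- **SAP 7.2:** state that nominal times govern the by-visit rows only, and that the per-subject summaries below use all post-dose assessments.
- **SAP 8.3 and Table 14.3.5:** for each Appendix F item, add the number and percentage of subjects by worst post-dose grade. Use every graded post-dose assessment, including unscheduled, early termination and Day 36 visits. Give the number of subjects with at least one such grade as the denominator.
- **SAP 8.6 and Tables 14.3.6.1 and 14.3.6.2:** add a matching row for any post-dose abnormality, by foot.
- **Guard against unequal opportunity:** beside each new row show the same count from the scheduled visits planned for everyone (T96h, Days 8, 15 and 29), and report by arm the number of unscheduled visits and of subjects with at least one.
- **Data check:** confirm whether the case report form records Appendix F grades at unscheduled visits. If it does not, say so in a footnote.

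The cost is a few SAP sentences and one extra panel per table. No visit, exam or clinical rule changes. The downside is the unequal number of exams per subject, which the paired rows and visit counts make visible but do not remove.

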7.3 Adjustments for Multiplicity

All efficacy endpoints will be listed in data listings. Unless otherwise indicated, two-sided p values will be reported.

If the outcome of the primary analysis of the primary efficacy endpoint ($AUC_{0\text{to}96\text{h}}$) is with a two-sided p-value of <0.05 , then key secondary endpoints will be compared between the 4.2 mg CA-008 and placebo. These key secondary endpoints are:

- Percentage of subjects who do not require opioids or are opioid free (OF) from T0 to T96): $OF_{0\text{ to }96\text{h}}$
- Total opioid consumption (in daily oral morphine equivalents) = OC from T0 to T96h: $OC_{0\text{ to }96\text{h}}$
- Using NRS at rest: $AUC_{0\text{ to }W1}$

Each of the above comparisons will be made using a two-sided test at the $\alpha=0.05$ level of significance. Once a p value of >0.05 occurs, all subsequent key secondary endpoints analyses in the hierarchy will be exploratory rather than confirmatory. All other efficacy analyses will be conducted using a significant 2-sided p-value of 0.05, without adjustment for multiplicity.

7.4 Efficacy Endpoints

CONFIDENTIAL

Efficacy will be evaluated using the numeric rating scale of pain intensity (NRS) scores (at rest and with ambulation), PGE, IGE, Rescue Use and Healthcare utilization. A variety of time-specific summed pain intensity assessments (area under the curve (AUC) for pain intensity) will be calculated using NRS to compare treatment difference between CA-008 and placebo group.

7.4.1 Primary Efficacy Endpoint

- Area under the curve (AUC) of the numeric rating scale of pain intensity (NRS) from 0 to 96 hours at rest ($AUC_{0 \text{ to } 96h}$).

7.4.2 Key Secondary Efficacy Endpoints

Following are key secondary endpoints (in descending order of importance):

- Percent of subjects who do not require opioids or are opioid free (OF) from 0 to 96 hours ($OF_{0 \text{ to } 96h}$)
- Total opioid consumption (OC) (in daily oral morphine equivalents) from 0 to 96 hours ($OC_{0 \text{ to } 96h}$)
- AUC of NRS through Week 1 at rest ($AUC_{0 \text{ to } w1}$)

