SC	Subcutaneous
SD	Standard deviation
SE	Standard error
SOC	System Organ Class
SNRIs	Serotonin-norepinephrine reuptake inhibitors
SSRIs	Selective serotonin reuptake inhibitors
T#	Time in hours after completion of study medication dosing (T0)
t ½	Elimination half-life
TEAEs	Treatment emergent adverse event[s]
TID	Ter in die (three times daily)
T max	Time to maximum plasma concentration
TRPV1	Transient receptor potential vanilloid-1
TFR	Time to first rescue
UDS	Urine drug screen[ing]
US	United States
V	Volume of distribution
W#	Week # visit after surgery
WHO	World Health Organization

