#### **9.1.5. Outpatient Phase: D8±1 (W1) Visit**

Subjects will return to the study center on D8±1 (W1) for the following assessments:

- Subject home diary review
- Document pain intensity (NRS) at rest and after ambulation (approximately 10 yards) each day since discharge from the inpatient unit
- Record vital signs (HR, BP and RR)
- Perform interim PE: surgical site assessment and neurosensory exam of the foot proximal to the surgical site with contralateral comparison
- Document concomitant medication use including doses and times taken for analgesic medications
- Document concomitant treatment use including topical ice pack or cooling treatments (only allowed during outpatient period)
- Record AE Assessment
- Obtain PGE assessment
- Obtain IGE assessment

In their diary, subjects will assess their current pain intensity at rest and after ambulation each morning (08:00 ±3 hours), and each evening (20:00 ±3 hours) using the NRS. The subject should be instructed to perform, if possible, the daily assessments as follows:

- Obtain the morning NRS assessment prior to taking any pain medication or approximately 2 hours after taking any pain medication
- Obtain the evening NRS assessment approximately 2 hours after taking any pain medication

Subjects should be instructed to record any medication they take (dose and time) whether to treat their pain or for any other reasons.

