In-Patient (Post Surgery)	Hours 0 (post-surgery), 24, 48, 72 and 96
Follow-up	Days 8(±1 day), 15(±2 days), 29(±2 days), 36(±2 days) ¹

¹ Day 36 visit will occur if insufficient wound healing is assessed by the investigator at the Day 29 visit.

All study assessments are outlined in Table 1 of the Protocol.

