For subjects who take prohibited medication, NRS results collected after taking the prohibited medication will not be used for AUC calculations but will be imputed according to the methods used for discontinued subjects.

Intermittent missing pain scores at rest or after ambulation (due to subject sleeping, etc.) will not be imputed, and AUC will be calculated based on non-missing values. For subjects who drop out of the study or take prohibited medication prior to Day 15, scheduled assessments will first be imputed using the worst prior pain score carried forward (WOCF).

Two sensitivity analyses will be performed to evaluate the robust of the primary result:

- 1) AUC will be calculated where assessments after drop out will be imputed using LOCF, using the last scheduled non missing pain score prior to drop out.
- 2) AUC will be calculated where assessments after dropping out will be imputed using the median score from the remainder of subjects in the group continuing in the study.

For secondary continuous efficacy endpoints, similar methods as the primary analysis will be used. For categorical endpoints, when assessments are imputed for data after a subject discontinues from the study, a WOCF method will be used.

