7.4.3 Other Efficacy Endpoints

- AUC of subject's NRS will be examined over various time periods: $AUC_{0 \text{ to } 6h}$, $AUC_{0 \text{ to } 12h}$, $AUC_{0 \text{ to } 24h}$, $AUC_{0 \text{ to } 120h}$, $AUC_{0 \text{ to } w1}$ (walking), $AUC_{0 \text{ to } w2}$, $AUC_{0 \text{ to } w2}$ (walking), $AUC_{12 \text{ to } 24h}$, $AUC_{24 \text{ to } 48h}$, $AUC_{24 \text{ to } 72h}$, $AUC_{24 \text{ to } 96h}$, $AUC_{96 \text{ to } 120h}$, $AUC_{96h \text{ to } w1}$, $AUC_{24h \text{ to } w1}$ (walking), $AUC_{96h \text{ to } w2}$, $AUC_{96h \text{ to } w2}$ (walking).
- Time-specific ("milestone") mean pain intensity NRS at 6, 12, 24, 28, 72, 96, 120, 144, and 168 hours
- Time-specific ("milestone") mean pain intensity NRS by site at 6, 12, 24, 28, 72, 96, 120, 144, and 168 hours
- OC over following time periods: $OC_{24 \text{ to } 48h}$, $OC_{24 \text{ to } 72h}$, $OC_{24 \text{ to } 96h}$.
- OF over following time periods: $OF_{24 \text{ to } 96h}$, $OF_{96h \text{ to } w1}$, $OF_{96h \text{ to } w2}$.
- Time to first use of rescue medication ($TTFR_{\text{after } T0}$) and first use after 24 hours ($TTFR_{\text{after } T24h}$). For the analysis of time to use of rescue medication, only OPIOID rescue medication will be considered,
- Analgesic consumption (AC) from T96h to W1 ($AC_{96h \text{ to } W1}$) and $AC_{96h \text{ to } W2}$.
- Patient global evaluation (PGE) comparing the percentage of subjects reporting (poor or fair) versus (good or excellent) responses and the percentage reporting each category of response at W1, W2 and W4.
- Investigator's global evaluation (IGE) comparing the percentage of those reporting (poor or fair) versus (good or excellent) responses and the percentage reporting each category at W1, W2 and W4.
- Number and percentage of subjects who drop out due to an AE or lack of efficacy (LOE) during the inpatient period: $LOE_{24 \text{ to } 96h}$, $LOE_{0 \text{ to } 96h}$.

- Health care utilization after discharge from the inpatient unit: HCU_{96h to W2} and HCU_{96h to W4}. (Not included in this SAP)

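### The key secondary AUC0 to W1 has no stated end hour and no rule for bringing each subject's pain curve to a common end

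*SAP*

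**What the plan says.** AUC0 to W1 at rest is the last of three key secondary endpoints, tested in a fixed order for 4.2 mg against placebo (Protocol 15.6.2, SAP 7.3). SAP 7.4.2 defines it only as "AUC of NRS through Week 1 at rest".

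- **Week 1.** The protocol's abbreviation list explains W# as "Week # visit after surgery", and Protocol 9.1.5 attaches W1 to a window: "Subjects will return to the study center on D8±1 (W1) for the following assessments". SAP Table 2-1 repeats that window, and SAP section 3 numbers the day of surgery as Day 0.
- **AUC rule.** SAP 7.5.2 sums trapezoids in NRS x hours and does not divide by the time observed. SAP 7.2 adds that "the ACTUAL TIMES will be used for the calculation of the AUC".
- **Missing scores.** Under SAP 7.1, intermittent missing scores "will not be imputed, and AUC will be calculated based on non-missing values". WOCF applies to subjects who drop out or take prohibited medication before Day 15.
- **Fixed hours nearby.** The milestone list in SAP 7.4.3 ends with "96, 120, 144, and 168 hours", but it concerns mean NRS and is not linked to this AUC.
- **Scores available.** Resting diary scores are due twice a day up to Day 15 (SAP 7.5.1). Protocol Table 1 also marks an NRS assessment at the Day 8 and Day 15 visits, on a separate row from the diary.

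The primary endpoint, by contrast, ends at a stated 96 h, where a score is compulsory whether or not the subject is asleep.

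**The concern.** An undivided AUC measures pain level multiplied by length of observation. Without a fixed end, length becomes part of the outcome. Two subjects with the same pain can get different values because they attended on different days. A subject who stays in the study but stops filling in the diary gets a lower, better value.

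Three end points fit the text: the actual visit, 168 h (the last milestone) and 192 h (nominal Day 8). The choice is therefore left to whoever programs the derivation. It also leaves open how far WOCF runs for someone who leaves before Day 8 and has no W1 visit. Protocol 15.1 promises that the SAP will say how variables are derived and how missing data are handled. For this endpoint, which is confirmatory if the hierarchy reaches it, it does not.

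**Working it through.** **1. The plan's own figure.** Neither document gives a sample size or power figure for AUC0 to W1. For AUC0 to 96h (difference 100, SD 130, two-sided 0.05, 90% power):
n = 2 x (1.960 + 1.282)² x 130² / 100² = 35.5, so 36 per arm. Power at 36 is 0.904 by the normal formula, and 0.896 (70 df) or 0.900 (140 df) by the t distribution. The stated 90% reproduces.

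**2. Length of the window.** With surgery on Day 0, Day 7 is 7 x 24 = 168 h, Day 8 is 192 h and Day 9 is 216 h. The spread is 48 h.

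**3. Effect of visit day, if W1 means the visit.** At constant pain, Day 9 minus Day 7 is 48 x NRS: 96, 144 and 192 NRS-h at NRS 2, 3 and 4 (assumed levels). As a worked case, assume T0 at 10:00, mean inpatient NRS 4 (96 x 4 = 384), outpatient NRS 3, and diary scores at 08:00 and 20:00.

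| Visit | Last score (h) | AUC0 to W1 |
|---|---|---|
| Day 7 | 166 | 384 + 3 x 70 = 594 |
| Day 8 | 190 | 384 + 3 x 94 = 666 |
| Day 9 | 214 | 384 + 3 x 118 = 738 |

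Fixed cut-offs at 168 h and 192 h differ by 24 x NRS, that is 48 to 96 NRS-h at NRS 2 to 4.

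**4. Effect of missing final entries.** Same case, Day 8 end, no visit score used:

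| Final entries missing | Last score (h) | AUC0 to W1 |
|---|---|---|
| 0 | 190 | 666 |
| 1 | 178 | 384 + 3 x 82 = 630 |
| 2 | 166 | 384 + 3 x 70 = 594 |
| 4 | 142 | 384 + 3 x 46 = 522 |

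Each lost entry removes 12 x 3 = 36. Removing two entries inside the curve changes nothing: the outpatient part is 282 either way, because the trapezoid bridges the gap.

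**5. Dropouts.** Running WOCF to 168 h rather than 216 h changes the value by 48 x worst score, for example 336 at an assumed worst score of 7.

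**6. Noise, if timing is balanced.** If 168, 192 and 216 h are equally likely, the SD of the end hour is √((24² + 0 + 24²)/3) = 19.6 h. Borrowing difference 100 and SD 130 from AUC0 to 96h (an assumption):

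| NRS | Added SD | Total SD | Power |
|---|---|---|---|
| 2 | 39 | 136 | 0.878 |
| 3 | 59 | 143 | 0.845 |
| 4 | 78 | 152 | 0.798 |

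A longer AUC will probably have a larger base SD, which makes the relative loss smaller. Assume outpatient NRS mean 3 and SD 1.5, independent of inpatient pain, and visits split 25/50/25 over Days 7, 8 and 9 (variance of the end hour 0.5 x 24² = 288). At a fixed 192 h the SD is √(130² + 96² x 1.5²) = 194. With variable timing it is √(130² + 96² x 1.5² + (3² + 1.5²) x 288) = 202, about 4% more.

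**7. Bias, if end-of-week loss differs by arm.** The shift in an arm mean is (excess share of subjects) x (hours lost) x NRS. For the last 48 h, an excess of 10 to 30 percentage points gives 0.10 x 48 x 2 = 9.6 up to 0.30 x 48 x 4 = 57.6. For one final entry at NRS 3, it gives 0.10 x 36 = 3.6 up to 0.30 x 36 = 10.8.

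**The case against.** The strongest reply is that nothing says the integral stops at the visit. Diary scores continue to Day 15, so data normally exist on both sides of any cut, and the 168 h milestone fits an ordinary week. That stands as far as it goes: the visit-day effect is conditional on one reading, although it is the reading the protocol's definition of W1 supports most directly. It does not supply an end hour.

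Second, an NRS recorded at the Day 8 visit would anchor the tail of a subject who stopped the diary but attended. This also stands, if the score is recorded and used. SAP 7.5.1 describes only diary scores for the outpatient period, so its use is not assured. A subject who resumes the diary later likewise has only an interior gap, provided later scores may be used to reach the cut.

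Third, WOCF already covers both dropouts and prohibited-medication users. The missing-tail problem therefore concerns subjects who remain in the study without either event.

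A reader might go further and infer that the plan biases the comparison, perhaps in favour of CA-008. The documents do not support that. Allocation is randomised and double-blind, the visit window is the same in every arm, and nothing indicates that timing or diary loss differs by arm. Nor should a 144-unit shift in one subject be read against the assumed difference of 100, which is a difference between arm means on a shorter AUC.

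**Conclusion.** The concern holds in a limited form. The endpoint cannot be computed uniquely from the text, and the stated missing-data rule scores lost final entries as less pain in subjects still in the study. Per subject, the size is up to 48 h x NRS across the visit window (if W1 is the visit) and about 12 h x NRS for each missing final entry with no later score. Between arms, the expected artefact under no treatment effect is zero when timing and loss are balanced, with a modest loss of precision. It is roughly 10 to 58 NRS-h if 10 to 30 percentage points more subjects in one arm lack the last 48 h. These figures rest on assumed outpatient NRS levels of 2 to 4; the documents give none.

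The reach is limited: the primary endpoint is untouched, and this endpoint is confirmatory only if the primary and the first two key secondaries succeed. It should still be settled before unblinding.

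**What to change.** In SAP 7.4.2 and 7.5.2, with a matching line in 7.1:

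- End AUC0 to W1 at T168h for every subject.
- Interpolate linearly to T168h using the next available resting score, from the diary or the Day 8 visit.
- If a subject still in the study has no later score, carry the last score to T168h. Make this the single prespecified rule. Dividing by observed hours would be a different estimand and should not be left as an alternative.
- Run WOCF for dropouts and prohibited-medication users to the same hour.
- Use the same end for AUC96h to W1 and the walking W1 AUCs.
- For the W2 AUCs, fix an end that in-window visits reach. The earliest visit within D15±2 is Day 13, about 13 x 24 = 312 h, so T312h is workable. T336h is not, because the diary is collected at that visit and about 24 h would have to be extrapolated. Where clock times leave the last score an hour or two short, the same carry-forward rule applies.

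Choosing 168 h over 192 h is a preference; what matters is one stated hour. The cost is a few sentences and a short change to derivation code, with no new data. The downside is that scores after the fixed end serve only for interpolation.
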